# 1.0 ABSTRACT

This two-phase project is designed to achieve the Cancer Moonshot objectives by reducing the burden of CRC on the US population. Specifically, we aim to improve CRC screening rates, follow-up colonoscopy, and referral to care in rural Medicaid patients by implementing a direct mail fecal testing program with targeted outreach and patient navigation for follow-up colonoscopy. We leverage partnerships with the Oregon Rural Practice-based Research Network (ORPRN), Kaiser Northwest Center for Health Research, and Medicaid Health Plans and deliver training and implementation support to participating rural primary care clinics using practice facilitation. For the pragmatic trial, we anticipate working with 3 CCOs and 30 clinics reaching approximately 4,500 Medicaid patients. For the scale up trial, we anticipate partnering with 20 organizations to facilitate program implementation with 130 primary care clinics (reaching 17,000+ rural Medicaid patients). The mailed FIT and patient navigation interventions will be implemented as part of standard care by health system or clinic staff.

In Phase I (Year 01), we will conduct a milestone driven pilot to build the necessary infrastructure for a large-scale trial, including adapting the clinic-health plan-vendor supported direct mail program for rural Medicaid patients that have not established care and/or never been screened; conducting a pilot study testing the feasibility and acceptability of patient navigation to support follow-up colonoscopy following an abnormal fecal test; engaging Medicaid Health Plans and recruiting 30 primary care clinics located in rural and frontier counties in Oregon; and developing the training and support materials needed to implement a large-scale trial in these settings.

In Phase II (Years 02-05), we will test our intervention using a two-arm cluster randomized control trial in 30 rural primary care clinics using program training and practice facilitation to support implementation. Participating clinics will be randomized into two groups: Intervention and Usual Care. Randomization will be stratified on health system. As in the pilot, the intervention combines: (1) a clinic-health planvendor supported direct-mail fecal testing program with targeted outreach for patients who have never been screened or who have yet to establish care and (2) patient navigation for those who are referred for colonoscopy as either the primary screening or for follow-up from an abnormal fecal test. We will evaluate effectiveness, implementation, and maintenance of the intervention through quantitative and qualitative measures. Results from the trial will inform scale-up of the program through partnerships with 20 regional and national organizations that serve rural/frontier primary care clinics using webinars, train-the-trainer workshops and collaborative learning activities.

# 2.0 BACKGROUND / RATIONALE

Colorectal cancer (CRC) is the third-leading cause of cancer deaths in the United States and the second leading cause among Oregonians. CRC is 90% curable with timely detection and appropriate treatment of precancerous growths. If not found until a patient is symptomatic, however, survival rates drop to 50%. However, 1 in 3 age-eligible adults is not up-to-date for CRC screening. Projections indicate that increasing CRC screening to 80% from current levels could prevent 277,000 cases and 203,000 deaths from the disease over the next 12 years. Achieving this goal will require concerted efforts as approximately 25 million US adults aged 50–75 (33%) are not currently up-to-date.

CRC screening rates are particularly low among adults in rural communities and sub-populations within these settings (e.g., Medicaid enrollees, Hispanic patients, Native Americans).  Rural areas cover 97% of the US land area and are home to approximately 60 million people. Within rural areas, frontier counties are the most remote and sparsely populated (having fewer than 7 people per square mile).  CRC incidence and mortality are disproportionately high among residents of rural regions;  disparities driven in part by differences in adherence to screening guidelines.  Medicaid enrollees are a key underserved group in rural areas. In 2016, Medicaid provided health insurance and access to preventive health services to 82 million people, including 1 million in Oregon.  Medicaid covers nearly 1 in 4 rural resident under age 65 (24%).  This is important as Medicaid members aged 50-64 years have relatively low rates of CRC screening, as demonstrated in national data (47% for Medicaid vs. 60% for private/Medicare aged 50-64)  and Oregon data for CRC screening in newly age eligible patients (34.9% for Medicaid vs. 42.8% for private).  Medicaid members also display less favorable CRC outcomes compared to commercially insured adults. 

Interventions are needed to address disparities is CRC screening, follow-up, and treatment in rural Medicaid patients. While mailed FIT and patient navigation are effective methods of improving screening and follow-up, no existing program incorporates these strategies into a resource-efficient, sustainable program that can be broadly implemented in rural geographic regions. Our study, Screening More patients for CRC through Adapting and Refining Targeted Evidence-based Interventions in Rural settings (SMARTER CRC), supports implementation of a targeted, multilevel program that incorporates tailored outreach, direct mail and patient navigation to address CRC disparities in rural Medicaid patients. A primary component of these interventions will be supporting collaborations between clinics, Medicaid health plans operating as ACOs, and commercial vendors to optimize and sustain program components. Through the course of a pilot test, large-scale pragmatic trial, and scale-up study, we anticipate working with 30 regional and national organizations to facilitate the program's implementation with an estimated 130 rural primary care clinics (17,000+ rural Medicaid patients). We will assess drivers of program success at the patient-, clinic-, and community-levels. SMARTER CRC will produce an implementation guide and resources to support program spread across rural settings serving Medicaid enrollees and other underserved populations.

SMARTER CRC is a partnership between faculty and staff at the Oregon Rural Practice-based Research Network (ORPRN) at Oregon Health & Science University (OHSU) and at the Kaiser Permanente Northwest Center for Health Research. This study fills key evidence and implementation gaps and supports Biden's Cancer Moonshot objectives by providing a model for how to rapidly adapt and scale-up multilevel interventions through clinic-health plan partnerships to reduce the burden of CRC on the US population.

# 3.0 OBJECTIVES

#### **Primary Objective:**

Adapt, pilot, then test the implementation and scale-up of targeted direct mail and patient navigation programs.

#### 4.0 STUDY POPULATION

The study team will recruit eligible CCOs and rural clinics, and we will work in turn with clinics to engage providers, staff, and patients. Our eligibility criteria for CCOs, clinics, clinics staff, patients and organizational partners are below.

CCOs/CCO staff: 1) serving a majority of counties that are predominantly rural based on 2010 RUCA Codes (Codes 4-10); 2) willing to participate in data collection activities (e.g., producing claims data, interviews).

Clinics: 1) Clinics will be eligible for the cluster randomization if there are 30 or more patients eligible for screening, 2) are classified as rural according to RUCA (Codes 4-10) or Oregon Office of Rural Health designations, 3) are served by CCOs agreeing to participate in the project; and 4) willing to implement the intervention into their clinic for the study.

Clinic Staff/Providers: 1) employed as a clinician or ancillary staff member in a participating clinic; 2) willing to participate in data collection activities (e.g., interviews, observation, surveys).

Patients: 1) attributed to participating clinic; and 2) are enrolled in Medicaid or Dual eligible; 3) eligible for CRC screening;

a. For the subset of patients that will be invited to participate in key informant interviews, a 5th eligibility criteria is consent to participate.

Exclusion criteria: Clinics are excluded if they have current or ongoing participating in other mailed fecal testing research projects in the Medicaid population. Patients are excluded if they are current for screening, have comorbid conditions that make patients poor candidates for screening based on clinical judgment (e.g., end-stage renal disease, enrollment in hospice), are not an established patient or for other reasons documented by the clinics.

Community or regional/organizational partners (includes endoscopy providers, community-based outreach workers, or leaders from regional or national organizations who participate in the pilot, pragmatic trial, or scale-up study) 1) involved in study activities (training, care delivery); 2) willing to participate in data collection activities (e.g., trainings, interviews, surveys).

For this project, we expect to recruit at least three CCOs and 33 Oregon clinics, which allows up to a 10% attrition rate to achieve our target of 30 rural primary care clinics. Based on Census Bureau data (https://www.census.gov/quickfacts/or), as of 2017, Oregon residents are 50.4% female and 13.1% Hispanic or Latino. Also based on Census data, Oregon resident diversity consists of 2.2% African American, 1.8% American Indian or Alaskan Native, 0.4% Native Hawaiian and other Pacific Islander, 4.7% Asian, 87.1% white, and 3.8% two or more races. Based on the Census Bureau's data, we expect the participating individuals to make up a representative sample of Medicaid individuals across the state.

# 5.0 INCLUSION/EXCLUSION CRITERIA

#### **Inclusion criteria:**

	Included	Excluded
Children		All patients we recruit will be at
		least 45 years of age or older, and
		clinic/CCO staff will be at least 18
		years of age or older.

Elderly	Yes – we anticipate that a limited number of clinic and CCO staff, or community organization representatives may be elderly; we limit our patient recruitment to those aged 45-75.	
Rural	Yes	
Inner City	No	
Low Income	Yes	
Disabled	Yes	
Chronic Care	Yes	
End of Life	Yes - This is possible, but we predict limited numbers because of the types of individuals we are recruiting: clinic and CCO staff, and patients who are not currently in hospice care.	
Minorities	Yes	
Both Genders	Yes	

This study will not include any vulnerable populations. We will not collect any information about subjects' status as prisoners, pregnant women, children, neonates, and/or adults lacking capacity.

# 6.0 METHODOLOGY

Throughout this trial we will collect data from multiple sources to assess process and outcomes data and drivers of program success at the patient-, clinic-, and community-levels aligned with a social ecological model for the quality of cancer care. These sources of data include:

- CCO interview, readiness assessment, and survey
- Clinic survey, readiness assessment, observation and interviews
- Patient interviews
- Interviews and surveys with regional and organizational partners
- Patient outcomes data (e.g., claims, vendor reports and electronic health record) and patient navigation registry data

# 7.0 STUDY PROCEDURES AND SCHEDULE OF EVENTS

CCO interview, readiness assessment, and survey: CCOs that express interest in participating in the trial will be invited to participate in a semi-structured interview (in-person or via phone) and complete a baseline survey to confirm CCO characteristics (e.g., size, number of primary care clinics in rural/frontier counties) as well as information about CCO data infrastructure, relationships with clinics, and quality improvement capacity. Readiness questions will be drawn from the literature and explore the CCO's prior experience with payment and quality improvement initiatives related to CRC screening and follow-up care.

Clinic survey, readiness assessment, observation and interviews: For clinics expressing interest in the trial, we will conduct semi-structured interviews (in-person or via phone) with clinic leadership to assess clinic characteristics, capacity and readiness to adopt the program and participate in the trial. Clinic characteristics will include descriptive data (e.g., ownership, primary care clinician number and FTE, EHR vendor and version), baseline CRC screening rates and if the clinic currently utilizes audit and

feedback, and details on current workflows related to CRC screening and follow-up (including provider CRC screening modality preferences). Capacity questions will explore general capacity as well as specific capacity related to CRC screening. Readiness questions will draw on prior work by Weiner, Hannon, and others, and utilize a clinic-level readiness survey piloted by our team during [name] K07.

We will conduct clinic surveys, interviews, and observations with clinic staff in various roles related to the program (e.g., outreach workers, patient navigators, quality improvement leads) to assess clinic/health system level factors that may influence outcomes. These assessments will happen at baseline and after implementation of the pilot as well as for each arm of the trial (post-implementation at 6-9 months as well as implementation context, maintenance, and sustainability approximately 12 months later [i.e., clinic exit interviews]).

Patient interviews: We will conduct one-on-one interviews with patients who receive the direct mail and patient navigation programs. Interviews will explore patient experiences with the program, including reaction, acceptability, satisfaction, and perceptions of usefulness; facilitators of, and barriers to, participating in the program and obtaining a follow-up colonoscopy; unintended consequences; and suggestions for improvement

Interviews and surveys with regional and organizational partners: To assess perceptions of the intervention and its impact on the broader community, we will interview CCO leaders, endoscopy providers (e.g., GI specialists, general surgeons, primary care clinicians) who treated study participants, and community organizations, including transportation service providers. Up to three interviews will occur throughout the duration of the study, including at baseline (pre-implementation), at the mid-point (approximately 12 months after the first-year implementation start), and post-implementation (approximately 12 months after the second-year implementation start). To evaluate the impact of scale-up activities we will conduct interviews and brief evaluation surveys with organizational leaders who participate in the trainings.

Patient outcomes data and patient navigation registry (Evaluation): Direct mail outreach and patient navigation activities will be tracked using reports from direct mail vendors, claims data from participating Medicaid health plans, clinic data from the electronic health record, chart abstraction data conducted by ORPRN or clinic staff, and data on navigation from a REDCap database. The mailed FIT and patient navigation interventions will be delivered by clinic and health plan staff as part of standard care. Clinics will be randomized to implement the interventions in different years to provide comparison groups. Claims data will be sent to the research team at OHSU from the participating payers based on their data pull of patients eligible for CRC screening in the clinics randomized to implement the intervention. Vendor reports will be sent to the CCO and research team based at OHSU. A clinic-level chart audit will be used to evaluate CRC screening and follow-up colonoscopy for patients with an abnormal FIT in intervention and control clinics.

Data for this project (i.e., process and survey data elements and patient navigation outcomes (such as number of patients who received patient navigation, number of patients with missed / canceled appointments or inadequate bowel preparation), will be stored in OCTRI's installation of REDCap, a highly secure and robust web-based research data collection and management system.

Features of REDCap that protect participants' privacy and data security include:

[figure not shown]
• Physical Security: OCTRI's REDCap software is housed on servers located in ITG's Advanced Computing Center providing locked physical security

- Electronic Security: The REDCap servers are housed behind both the OHSU firewall and a second ACC firewall. All transmissions of data from the application are encrypted over HTTPS with the industry standard TLS 1.1 protocol (AES 256-bit encryption).
- Controlled User Access: REDCap employs a robust multi-level security system that enables researchers to easily implement "minimum necessary" data access for their research staff, including specification of data fields that are identifiers. This feature includes "single click" ability to provide completely deidentified (removing all identified data fields and shifting dates) for analysis or other purposes. User activities are logged to enable auditing of all data access. Access is integrated with OHSU's network such that users who are also OHSU employees are authenticated against their OHSU network credentials.
- Data Integrity: REDCap is jointly managed in accordance with OHSU Information Security Directives by ACC staff and members of OCTRI's Biomedical Informatics Program, ensuring fidelity of database configuration and back-ups. User activities are logged to enable auditing of all data changes.

Data from the vendor and REDCap database will be merged with claims data to generate evaluation reports. To avoid bias in colonoscopy capture across baseline and follow-up time-points, ORPRN practice facilitators will perform a chart audit on all patients who were eligible for the direct mail program. The chart audit will confirm FIT completion and monitor for colonoscopy referral and receipt, pathology results, and referral to care (i.e. surveillance or cancer treatment), as indicated.

Researchers are requesting a waiver of authorization to access medical record data. ORPRN study staff plan to conduct the chart audit at each clinic over the course of 1-3 days. Data will be stored on the OHSU instance of REDCap or stored securely on OneDrive and ORPRN staff and select Kaiser Permanente research team members will have access to the data by utilizing a password-protected file on OneDrive or a REDCap user login. OneDrive and REDCap user permissions will be matched to roles as described in the established Data Use Agreement between Kaiser Permanente and OHSU and to the IRB. PHI will never be disclosed outside of the study team and all PHI will be destroyed upon completion of the study. Through data use agreements, a limited dataset will be shared with the sponsor, the National Cancer Institute. The following data elements will be included in the limited data set: patient identifier, age group, sex, Hispanic or Latino origin, race, state of residence, county of residence and primary health insurance. When possible, the data set will also include primary language, ZIP code of residence, individual history of CRC, most recently performed screening test date and result, and diagnostic colonoscopy date and result.

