recruit clinics; conduct	exclusion criteria for CCOs and clinic	literature,	board on inclusion and exclusion	2020		
baseline assessment; use	participation in Phase II.	statistical power	criteria			
results from pilot to		requirements				
prepare to conduct a	b. Develop CCO and clinic	Relevant	Feedback from local advisory	Jan – Mar		
large-scale, pragmatic	recruitment materials	literature	board	2020		
implementation-	b. Successfully engage 3 CCOs and 30	Feasibility data	List of participating CCOs and	Mar – Sep		
effectiveness trial and	rural/frontier clinics for the main trial	from pilot study	selected clinic characteristics	2020		
scale-up (see Phase II).	d. Develop manual outlining trial	Feasibility data	Feedback from advisory board on	Apr – Sep		
	protocols (including quality assurance	from pilot study	recruitment materials; study	2020		
	protocols), scopes of work, and		protocol; scope of work			
	associated budgets.					

Aims	Assessment/	Data Sources	Description	Timeline
	Measurement			
Aim 1. Conduct a large-scale pragmatic study, cluster randomized control trial, to assess the implementation, effectiveness, and maintenance of the program piloted in Phase I in 30 rural primary care clinics (n ~ 3,960 patients aged 45 – 75) using practice facilitation to support implementation. Using a mixed methods approach, identify patient-, clinic/health system-, and payer/policy/community-level factors that are associated with reach, effectiveness, implementation and maintenance	Assessment of effectiveness (patient and clinic level).	Administrative data, claims data, EHR data from clinics, vendor data, laboratory data, survey data.	Patient Level Outcome (Primary): Completion of any CRC screening Clinic Level Outcome: Proportion of Medicaid patients screened for CRC We will compare the intervention vs. control clinics after adjusting for baseline at 6 and 12 months. The primary endpoint is 6 months. Secondary outcomes: completion of testing types (fecal testing, FIT-DNA, CT Colonography, Colonoscopy, Flex Sigmoidoscopy; patient level) and % completion (clinic level); time to screening from study-eligible patient list pull (patient level); FIT results (patient level); follow-up colonoscopy completion (patient level); time to colonoscopy from abnormal FIT result (patient level); and adenomas or cancers detected (patient level).	2021-Sep 2024

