and to assess program adaptations.	Assessment of implementation (compliance rate with program components at clinic level).	Administrative data, claims data, vendor data, laboratory data, survey data including debriefs.	Proportion of core activities performed (e.g., mailed FITs, patient navigation calls) by clinics/CCOs	2021-2024
	Assessment of maintenance (compliance rate with program over time at clinic level).	Administrative data, claims data, vendor data, laboratory data, survey data.	Proportion of intervention clinics sustaining program in second year (N core activities sustained in second year/ N core activities, in intervention clinics/CCOs). Effectiveness of the program in intervention clinics in Year 2.	2021-2024
	Assessment of maintenance (compliance rate with program at patient level)		Proportion of patients who completed FIT in Year 1 who complete in Year 2, in intervention clinics.	

	Assessment of program second year implementation and adaptations.	Clinic/CCO surveys and interviews.	Types of and reasons for program adaptations, based on Wiltsey-Stirman FRAME framework.	May 2023- Sep 2024
Aim 2. Partner with regional and national organizations ( $n\sim20$ ) to scale-up the program to additional clinics serving rural and underserved patients in high priority geographic regions of the US ( $n\sim130$ clinics; 17,000+ patients) using webinars, trainthe-trainer workshops and collaborative learning approaches. Assess trainings delivered, program adoption and adaptations and determinants of dissemination success.	a. Assessment of adoption by clinics and community organizations.	Participation in workshops, training, and collaborative learning activities; survey data; use of	N clinics, community organizations, and staff that participate in training workshops, train-the-trainer sessions, and collaborative learning activities.  Adoption as reported on 6-month survey data of workshop participants.	2021-2024
		program tools and implementation materials.	Use of program tools; downloads of training and implementation materials.	
	b. Assessment of program adaptations.	Clinic and community organization surveys and interviews.	Types of and reasons for program adaptations.	Oct 2023- Sep 2024

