The primary effectiveness outcome of this study at the patient level is the completion of any colorectal cancer (CRC) screening (for study-eligible patients). Consistent with the pragmatic nature of the trial, we will use claims, vendor data, and EHR data for calculating CRC screening outcomes. Comparing the likelihood of receiving CRC screening between intervention and usual care groups at 6-month post participant list-pull date, we hypothesize that CRC screening will be more likely in patients allocated to the intervention group versus the usual care group. To examine the effectiveness of the program CRC screening completion at 6 months, we will use the generalized form of the hierarchical linear model (HLM; using a logit link and binomial distribution, aka multilevel logistic regression) to account for the clustering of patients within clinics and the assignment to arm at the clinic level. The variables that will be included in the model are the clinic baseline screening rate (if available) and a binary indicator of arm (1=tailored, 0=standard) as fixed effects and clinic is a random effect. A positive and significant coefficient for arm would provide support for the effectiveness of the intervention. We will do a moderator analysis at all levels to explore the impact of patient and clinics characteristics (see outcomes table above), and implementation components affecting outreach on completion likelihood in groups of patients determined at analysis (e.g. never screened, Hispanic, etc.).

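### If usual-care clinics adopt the program in a later year, is the time-to-screening comparison contaminated because it has no stated horizon?

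*Combined protocol and SAP*

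**What the plan says.** The Abstract (Section 1.0) states "Participating clinics will be randomized into two groups: Intervention and Usual Care", and Section 9.0 repeats it. Neither section says that usual-care clinics later receive the program. Section 7.0, on patient outcomes data, says "Clinics will be randomized to implement the interventions in different years to provide comparison groups". The clinic-survey text of the same section plans assessments "as well as for each arm of the trial (post-implementation at 6-9 months", with a further look about a year later, which fits both arms implementing at some point.

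Section 8.0 places the first year of implementation in 2021 and the second in Spring 2022, without saying which clinics the second refers to. The Phase II table in that section uses the same vocabulary for the intervention arm: "Proportion of intervention clinics sustaining program in second year" and "Effectiveness of the program in intervention clinics in Year 2".

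On timing of outcomes, the table says "We will compare the intervention vs. control clinics after adjusting for baseline at 6 and 12 months" and names 6 months as primary. It then lists secondary outcomes, among them "time to screening from study-eligible patient list pull (patient level"). Section 9.0 sets the primary contrast as "Comparing the likelihood of receiving CRC screening between intervention and usual care groups at 6-month post participant list-pull date" and gives a multilevel logistic model for it. That section also plans six data transfers, every 6 months from Spring 2021 to Fall 2023, so that up to 18 months can be captured after each mailing.

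**The concern.** Read on its own, the Section 7.0 sentence means that every randomized clinic implements and that the comparison comes from timing. The statistical section never describes that design. No section gives a list-pull date, a start date for comparison clinics, or a rule that closes the between-arm comparison at such a start. Time to screening has an origin, the list pull, but no end of follow-up, censoring rule or model.

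An analyst could therefore run the curves over all captured data. After the comparison clinics start, the contrast would set an arm in its second program year against an arm in its first, with the latter still labelled usual care. A late narrowing of the curves might then be read as the effect fading. The same question arises for the 12-month comparison and, with late enough list pulls, for the primary endpoint.

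**Working it through.** **Inputs from the documents.** Recruitment in Fall/Winter 2020-2021, first-year implementation in 2021 and second-year implementation in Spring 2022 (Section 8.0); data transfers every 6 months from Spring 2021 to Fall 2023, six in all, with up to 18 months captured after each mailing (Section 9.0); arm comparisons at 6 and 12 months (Section 8.0).

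**The plan's own figure.** From Spring 2021 to Fall 2023 is 30 months, and 30 / 6 + 1 = 6 transfers, as stated. Fall 2023 is 18 months after Spring 2022, so the schedule fits a mailing in 2021 and another in Spring 2022. It does not show which clinics receive the second.

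**Assumptions.** List pulls in March, April or May 2021. This is the best-anchored period, since it follows recruitment and coincides with the first data transfer, but it is not stated. Comparison clinics start in March, April or May 2022, which is an inference from Section 8.0.

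**Formula.** With January 2021 = month 1, overlap = max(0, pull month + horizon - start month). Pulls are months 3, 4, 5; starts are months 15, 16, 17.

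*6 months (primary).* Windows close in months 9, 10 and 11. The smallest gap to a start is 15 - 11 = 4 months and the largest is 17 - 9 = 8. Overlap is 0 in all 9 combinations.

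*12 months.* Windows close in months 15, 16 and 17:

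| Pull | March start (15) | April start (16) | May start (17) |
|---|---|---|---|
| March (3) | 0 | 0 | 0 |
| April (4) | 1 | 0 | 0 |
| May (5) | 2 | 1 | 0 |

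Overlap occurs in 3 of 9 combinations, by 1 or 2 months. These are calendar overlaps and hence upper limits, because kits must still be mailed and returned before a program screening is recorded.

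*18 months.* The same formula gives 3 + 18 - 17 = 4 to 5 + 18 - 15 = 8 months. This figure carries little weight. The 18 months in Section 9.0 is a data-capture span counted from each mailing, not from list pull; patients in usual-care clinics have no first-year mailing; and no section plans an 18-month comparison of arms.

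**Sensitivity to the pull date.** With the earliest assumed start (month 15), the 6-month window is clear when pull + 6 is at most 15, that is, for pulls up to September 2021. For pulls anywhere in 2021 and the same three starts, overlap ranges from 0 to 3 months at 6 months and from 0 to 9 at 12 months.

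**What must hold for harm.** (a) Comparison clinics start the program; (b) they do so in about Spring 2022; (c) the time-to-screening comparison runs past that start; (d) patients on the original comparison list are reached by the later program. Section 7.0 supports (a). The documents establish none of (b), (c) or (d).

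**The case for a change.** The strongest case for acting is that the gap is real and cheap to close. The Section 7.0 sentence is plain, and assessments after implementation in each arm make little sense for an arm that never implements. Neither the 6- nor the 12-month time point is tied explicitly to time to screening. An unspecified horizon leaves a choice that could be made after seeing the curves, and closing it takes only wording and a cut-off date.

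Most of this stands as description: the plan does not say whether or when usual-care clinics start, nor where the time-to-screening comparison ends. It does not stand as a contradiction, because usual care followed by a delayed start is a coherent design and Section 7.0 itself discloses the staggering. The Spring 2022 date can equally be read as the intervention clinics' second year, given how the maintenance rows use the term. The table cell that lists time to screening opens by comparing arms at 6 and 12 months, so 12 months is the natural outer limit, although it is not spelled out. Nor can the size or net direction of any distortion be derived, since intervention clinics also continue into a second year.

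**Conclusion.** This is missing detail that analysts can fill sensibly; it does not call for a change to the plan. The primary contrast is fixed at 6 months from list pull and, for Spring 2021 pulls with a start in March to May 2022, closes 4 to 8 months before any comparison clinic could begin. The 12-month comparison is touched in 3 of 9 combinations, by at most 2 calendar months. Where that happens, a comparison by allocated arm remains valid as early versus delayed start.

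What is left is one secondary outcome with no hypothesis or model attached. Those running the analysis will know the actual pull and start dates, and would ordinarily end the between-arm curves in both arms no later than 12 months or the comparison clinics' start.

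The conclusion rests on Spring 2021 list pulls. Pulls in October 2021 or later could bring the primary window into play, by up to 3 months under the assumed starts, but nothing in the documents points to pulls that late.
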